9.0 ASSESSMENT OF SAFETY

9.1 Safety Assessments

- AEs: Spontaneously reported AEs; either volunteered by the patient, prompted by non-directed questioning or reported by an investigator will be documented on the eCRF.
- Standard 12-lead ECG
- Safety Laboratory Tests (Serum chemistry, hematology, urinalysis)
- Vital Signs and Physical Examination

9.1.1 Discontinuation of Study Drug

Study drug will be discontinued for any subject who experiences:

- a diagnosed IBD flare up based on clinical judgment or the partial Mayo score

- cholangitis
- biliary strictures
- drug-induced liver injury (DILI, see below)

Drug-induced liver injury (DILI)

Cholestatic markers (ALP/GGT) need to be monitored closely for emergent complications of PSC and/or disease progression. To protect patient safety, sites will be instructed to closely monitor for DILI of all subjects as defined by the following criteria:

- Normal total bilirubin throughout the trial and only transaminase elevations are observed:
 - ALT or AST increase $\geq 5X$ baseline levels AND the patient doesn't have liver-related symptoms or immunological reaction, e.g. anorexia, nausea, vomiting, right upper quadrant pain, rash and pruritus (but not confined to these clinical features only)
 - ALT or AST increase $\geq 3X$ baseline levels AND are associated with liver-related symptoms or immunological reaction, e.g, anorexia, nausea, vomiting, right upper quadrant pain, rash and pruritus (but not confined to these clinical features only)
- Increase in total bilirubin $\geq 2X$ baseline AND exceeds 2X ULN with or without liver-related symptoms or immunological reaction, e.g. anorexia, nausea, vomiting, right upper quadrant pain, rash and pruritus (but not confined to these clinical features only)
- ALP or GGT that increase to 3X baseline without OR 2X baseline with liver-related symptoms or immunological reaction, e.g. anorexia, nausea, vomiting, right upper quadrant pain, rash and pruritus (but not confined to these clinical features only)
- INR increased by at least 50% above baseline level to abnormal value.

For the subjects described above, the study drug will be discontinued, the liver profile tests (ALT, AST, bilirubin and PT/INR) will be repeated within 2-3 days along with a physical examination. The AE will be followed per adverse event reporting instructions and a report form will be completed accordingly. All cases will be reviewed by the DURECT Safety Assessment Committee (SAC), see Section [13.6](#).

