7.4 Study Stopping Criteria

In the event a subject experiences grade 5 CTCAE toxicity, the study will be paused and safety reports will be submitted to FDA for review and agreement prior to dosing any further subject.

If more than 2 subjects develop a CTCAE grade 3 or higher in the same category, the study will be paused and safety data will be evaluated to determine the next step.

Based on the above evaluations, the study may proceed or may be stopped in accordance with the SAC Charter (see Section 13.6, Safety Assessment Committee).

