9.13.2 Classifications

Severity

The Investigator will evaluate the intensity of each adverse event using the following definitions:

- Mild: An event that is easily tolerated by the subject, causing minimal discomfort and not interfering with everyday activities (CTCAE Grade 1).
- Moderate: An event that is sufficiently discomforting to interfere with normal everyday activities (CTCAE Grade 2).
- Severe: An event that prevents normal everyday activities (CTCAE Grade 3-5).

Adverse events should be assessed according to the National Cancer Institute Common Terminology Criteria for Adverse Events (CTCAE) Version 4.0.

In the event of the occurrence of a severe adverse event, the Investigator will be instructed to immediately inform the sponsor for follow-up steps.

An AE that is assessed as severe should not be confused with an SAE. Severity is a category utilized for rating the intensity of an event; and both AEs and SAEs can be assessed as severe. An event is described as ‘serious’ when it meets one of the pre-defined outcomes as described in Section 9.13.1.

Causality

A blinded Investigator is obligated to assess the relationship between test drug and the occurrence of each AE/SAE. The Investigator will use clinical judgment to determine if there is a reasonable possibility that the pharmacological action of the test drug was responsible for the AE/SAE being reported. Alternative causes such as natural history of the underlying diseases, concomitant therapy, other risk factors, and the temporal relationship of the event to the test drug will be considered and investigated. The Investigator will also consult the Clinical Investigator’s Brochure and/or Product Information, for marketed products, in the determination of his/her assessment.

After careful medical consideration, the Investigator will evaluate the relationship of each adverse event to test drug applying the following definitions:

Probably Related – Good reasons and sufficient documentation to assume a causal relationship

Possibly related – A causal relationship is conceivable

Unlikely related – The event is most likely related to etiology other than the test drug

Not Related – Good reasons and sufficient documentation to exclude a causal relationship.

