13.5 Data Safety Monitoring Committee

A Data Safety Monitoring Committee has not been planned for this open-label trial. Periodic reviews of safety data will be performed by the Sponsor's medical monitor.

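### The ALT/AST stopping rule in 9.1.1 applies only while total bilirubin is normal, so the same rise with bilirubin above 1× and up to 2× ULN triggers no DILI stop unless another criterion is met

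*Combined protocol and SAP*

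**What the plan says.** Section 9.1.1 lists events for which study drug must be stopped: IBD flare, cholangitis, biliary strictures and drug-induced liver injury (DILI). For DILI, "sites will be instructed to closely monitor for DILI of all subjects as defined by the following criteria". Four criteria follow:

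- **Transaminases.** The heading condition is "Normal total bilirubin throughout the trial and only transaminase elevations are observed". Under it sit two thresholds: ALT or AST at least 5× baseline without symptoms, or at least 3× baseline with liver-related symptoms or an immunological reaction.
- **Bilirubin.** An increase to at least 2× "baseline AND exceeds 2X ULN with or without liver-related symptoms or immunological reaction".
- **Cholestatic enzymes.** "ALP or GGT that increase to 3X baseline without OR 2X baseline with liver-related symptoms or immunological reaction".
- **INR.** A rise of at least 50% over baseline, to an abnormal value.

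Meeting a criterion stops the drug. It also triggers repeat liver tests within 2-3 days, a physical examination and review by the Safety Assessment Committee (SAC).

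**The concern.** The ALT/AST rule switches off as soon as bilirubin leaves the normal range, and the bilirubin rule does not switch on until 2× ULN is exceeded. Between the two, a transaminase rise that would force a stop at normal bilirubin forces nothing, although the liver picture is worse. The repeat tests, examination and SAC review in 9.1.1 attach to the same criteria, so that section does not require them for such a subject either.

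Safety is a primary objective (5.1) and the subjects have liver disease. Chemistry is drawn about weekly during treatment (7.3.3), so the rise would be seen, but no visible subject-level rule would then say stop. What remains is:

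- investigator discretion (14.4.1);
- notice of severe events, where "the Investigator will be instructed to immediately inform the sponsor for follow-up steps" (9.13.2);
- medical-monitor oversight: "Periodic reviews of safety data will be performed by" that monitor (13.5);
- a study-level pause: "If more than 2 subjects develop a CTCAE grade 3 or higher in the same category", or after any grade 5 event (7.4).

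**Working it through.** The plan gives no figure to reproduce, so the check is of the rule's logic.

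**Inputs, all from 9.1.1.** Let A be ALT or AST as a multiple of baseline, b baseline bilirubin and x current bilirubin (both in multiples of ULN), and P the larger of ALP and GGT as multiples of baseline.

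- T (transaminase): b ≤ 1 and x ≤ 1, no other elevation, and A ≥ 5, or A ≥ 3 with symptoms. This takes the bilirubin condition as normal to date, the more generous reading, because a condition on the whole trial cannot be judged at a visit.
- B (bilirubin): x ≥ 2b and x > 2.
- C (ALP/GGT): P ≥ 3, or P ≥ 2 with symptoms.
- I (INR): at least 1.5× baseline and abnormal.

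**Bounds of the gap.** For b ≤ 1, 2b ≤ 2, so the binding part of B is x > 2. T fails once x > 1. With C and I not met, no criterion holds for 1 < x ≤ 2. Divided by b, that is a bilirubin rise of more than 1/b and up to 2/b times baseline:

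| Baseline bilirubin (× ULN) | Gap (× baseline) |
|---|---|
| 0.4 | above 2.5, up to 5.0 |
| 0.5 | above 2.0, up to 4.0 |
| 0.8 | above 1.25, up to 2.5 |
| 1.0 | above 1.0, up to 2.0 |

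**Grid check.** With b = 0.5, 0.8 and 1.0, and ALT at 5× without symptoms, 3× with and 10× with, every combination stops at x = 1.00, none at 1.01, 1.5 or 2.00, and every one at 2.01.

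**Worked cases.** ALP, GGT and INR are unchanged, with no cholangitis, stricture or IBD flare.

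| ALT (× baseline) | Symptoms | Bilirubin (× ULN), baseline to now | As written | Condition deleted |
|---|---|---|---|---|
| 8 | no | 0.8 to 0.9 | stop (T) | stop |
| 8 | no | 0.8 to 1.2 | no stop | stop |
| 8 | no | 1.0 to 1.8 | no stop | stop |
| 8 | no | 0.5 to 1.9 | no stop | stop |
| 20 | no | 0.5 to 1.5 | no stop | stop |
| 8 | no | 0.8 to 2.1 | stop (B) | stop |
| 4 | yes | 0.8 to 0.9 | stop (T) | stop |
| 4 | yes | 0.8 to 1.5 | no stop | stop |

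Three of the eight stop as written. All eight stop with the condition deleted, necessarily, since each was chosen with ALT over its threshold. The table shows where the rule fails, not how often. In the fourth row bilirubin is 1.9/0.5 = 3.8× baseline and still meets nothing.

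**Exposure.** Dosing runs to Day 28 (7.2.1), so 28 minus the visit day gives the scheduled doses left after that day: 20 from Day 8, 13 from Day 15 and 6 from Day 22, plus up to 2 extra if the last visit falls on Day 30. These are upper bounds. They assume that the subject stays in the gap at later visits and that nobody stops earlier, and they include doses taken while the central-laboratory result is awaited.

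**Related ambiguity.** Taken strictly, the word limiting the heading to transaminase elevations also disables T when ALP or GGT rises below its own trigger. ALT 8× without symptoms and ALP 2.5× baseline, or ALT 4× with symptoms and ALP 1.8×, would then not stop even at bilirubin 0.9× ULN. Taken loosely (no other criterion met), both stop. The loose reading is the workable one, because every subject enters with ALP at least 1.5× ULN (5.3.1). The bilirubin gap is the same under either reading.

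**The case against.** The heading could be a scenario label for an isolated transaminase rise rather than a deliberate switch, and the sponsor may have meant any such rise to stop the drug. That is possible, but DILI is defined by the listed criteria and none covers this pattern. Intent that is not in the text does not bind a site.

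The flare stop is worded "a diagnosed IBD flare up based on clinical judgment or the partial Mayo score", and the contrast with the DILI list might suggest that judgment is excluded for DILI. This is weak support, since cholangitis and strictures also carry no criteria and can only be clinical diagnoses. The point rests on the definition by listed criteria instead.

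Other provisions expect a response to such a result. Section 9.13.1 makes a laboratory change needing active management an adverse event and names stopping the drug among the possible actions. Section 9.5.1 requires clinically significant values to be followed and treated as appropriate, and 14.4.1 lets the investigator end participation. These reduce the consequence but leave the stop to discretion.

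A bilirubin rise may reflect PSC rather than the drug. Cholangitis and biliary strictures are themselves mandatory stops, however, so this is no reason for continued dosing.

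Two limits stand. The worked cases hold ALP, GGT and INR fixed, which excludes the alternative stops by assumption. Part of the SAC text (13.6) is blacked out, and the SAC charter, Table 1 and the appendices cannot be seen, so the most that can be said is that no visible subject-level rule fills the gap.

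**Conclusion.** The concern holds. For a subject with baseline bilirubin at or below ULN, a transaminase rise over the plan's own threshold requires no DILI stop while bilirubin is above 1× and up to 2× ULN, however high ALT goes, unless another criterion in 9.1.1 is met. The same rise with normal bilirubin does require a stop. This is an error in how the rule runs rather than a missing detail, because following it gives the less safe action for the worse picture.

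The conclusion rests on the unredacted wording of 9.1.1 and on reading the bilirubin condition as normal to date. No claim is made for subjects entering above ULN, because the entry cut-off is blacked out. The documents give no basis for estimating how many of the 40 subjects, if any, would fall in the gap.

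**What to change.** Delete the heading condition on the transaminase criterion, so that ALT or AST at least 5× baseline, or at least 3× with symptoms, requires stopping at any bilirubin, ALP or GGT level once the central-laboratory result is reported. This also removes the ambiguity about other enzyme rises. Whether a combined ALT and bilirubin rise deserves a stricter threshold is for the sponsor's medical team.

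The cost is one line of protocol text and no new scheduled test, with possibly a few more mandatory discontinuations. Stopping drug does not remove a subject from the mITT population (11.3). A subject who also left the study would use one of the 40 − 36 = 4 early withdrawals that the sample size allows (11.1).

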9.2 Interim Safety Profile

There is no interim safety analysis planned for this study.

9.3 Adverse Event Recording

Adverse events will be recorded from the time the patient signs the informed consent form through trial completion final visit/early termination.

9.3.1 Spontaneously Reported Adverse Events

Spontaneously reported AEs; either volunteered by the patient, prompted by non-directed questioning or reported by an investigator will be documented on the eCRF.

9.4 12-Lead ECGs

Standard resting 12-lead ECGs will be obtained according to the schedule of events. Overall interpretation will be recorded on the eCRF. Clinically significant ECG findings that emerge after treatment will be recorded on the AE eCRF.

9.5 Laboratory Tests

All routine laboratory analyses will be conducted by a central laboratory and have been listed below. Laboratory tests will be obtained as indicated on the Schedule of Events table. Instructions on sample collection, processing and shipment will be provided in a separate laboratory manual.

PPD/CCI

Female subjects of childbearing potential will have a urine pregnancy test at Screening, Day 1, Day 28 and at the end of the study. The urine pregnancy test will be performed locally at the investigative site.

9.5.1 Safety Laboratory Tests

Chemistry: Sodium, potassium, chloride, bicarbonate, serum bile acids (total and sub-speciation), serum creatinine, urea, glucose, albumin, calcium, uric acid, alanine aminotransferase, alkaline phosphatase, aspartate transaminase, creatine kinase (CPK), bilirubin (total and conjugated), cholesterol (total, LDL and HDL), triglycerides and gamma-glutamyl transpeptidase (GGT).

Hematology: White cell count with differential (neutrophils, lymphocytes, monocytes, eosinophils, basophils), red blood cell count, hemoglobin, hematocrit, platelet count, mean platelet volume, mean corpuscular volume, mean corpuscular haemoglobin, mean corpuscular haemoglobin concentration, red cell distribution width.

Coagulation: PT (INR)

Urinalysis: Macroanalysis by dipstick for glucose, bilirubin, ketones, blood, pH, protein, and urobilinogen.

Other: Hepatitis B surface antigen, Hepatitis C antibody *HIV 1/HIV 2 and IgG4.

Laboratory values that are out of range for the central lab will be identified and may be repeated at the Investigator's discretion. The Investigator will classify laboratory values outside the normal range as either clinically significant or not clinically significant. Clinically significant laboratory values outside the normal range (i.e. any clinical abnormality or change that suggests a disease and/or organ toxicity and is of a severity that requires active management) that emerge after signature of the Informed Consent Form will be considered and recorded as an AE. Clinically significant out of range laboratory values that emerge after treatment will be followed and treated (if appropriate) by the Investigator until resolution or lost to follow-up.

9.6 Biomarkers

A PPD/CCI sample will be collected at screening visit PPD/CCI and at pre-dose at Day 1, Day 8, Day 15, Day 22, Day 28, Day 42 and Day 56 (or early termination visit) for assessment of selected exploratory biomarkers.

PPD/CCI

Where time-points of different sample or test types coincide then the following sequence applies:

- Vital Signs
- ECG
- Biomarkers (serum)
- PK (plasma- at selected sites)
- Safety lab tests

Details on sample collection, processing, storage and shipment will be provided in the study specific Study Reference Manual.

9.7 Vital Signs

Systolic/diastolic blood pressure, heart rate, respiratory rate, and temperature will be measured. Blood pressure and heart rate will be measured after the patient has been resting (supine or sitting) for 5 minutes. Measurements will be taken at the times specified in the Schedule of Events table and will be recorded on the appropriate source document and eCRF.

9.8 Physical Examination

A Complete Physical Examination will be conducted at Screening, ,Day 1, Day 28, and at the Trial Completion Visit (Study Day 56) or Early Termination Visit. Day 1 Complete Physical Exam will establish a baseline for comparison with findings at subsequent study visits.

The Complete Physical Exam includes the following assessments:

- Weight
- Height (at screening only)
- General Appearance: head, eyes, ears, nose, mouth, throat, neck (including thyroid)
- Cardiovascular System
- Respiratory System
- Gastrointestinal and Liver System, including rectal examination where indicated
- Skin
- Musculoskeletal System
- Lymph Nodes
- Neurological System

A Limited Physical Exam (excluding height) will be conducted at Day 8, Day 15, Day 22, and Day 42. It includes the following assessments:

- Weight
- General Appearance: head, eyes, ears, nose, mouth, throat, neck (including Thyroid)
- Gastrointestinal and Liver System, including rectal examination where indicated
- Any other body system at the PI's discretion

For unscheduled visits, complete or limited physical exam will be conducted at the PI's discretion.

Any changes from baseline outside the normal range that emerge after treatment will be recorded on the AE eCRF.

9.9 Partial Mayo score

The partial Mayo score ([Rutgeerts et al, 2005](#)) will be collected at each study visit ([Appendix 5](#)). This score consists of stool frequency, rectal bleeding, and Physician's Global Assessment (PGA). It aids in the assessment of an IBD flare.

9.10 Blood and Urine Sampling

Blood and urine samples will be collected for safety and biomarker tests from all subjects as per target sample times ^{PPD/CCI} [REDACTED]

A urine pregnancy test (for female with childbearing potential) will be collected at screening visit, Day 1 visit, Day 28 visit and end of study/early termination visit.

PPD/CCI [REDACTED]

[REDACTED]

[REDACTED]

[REDACTED]	[REDACTED]	[REDACTED]	[REDACTED]	[REDACTED]	[REDACTED]
[REDACTED]	[REDACTED]	[REDACTED]	[REDACTED]	[REDACTED]	[REDACTED]

9.11 VAS Itch Score and 5-D Pruritus Itch Scale

The VAS (Visual Analogue Scale) Itch Score evaluates the subject's severity of itching ([Appendix 3](#)). The 5-D Pruritus Itch Scale is developed as a brief but multi-dimensional questionnaire designed to be useful as an outcome measure in clinical trials ([Appendix 4](#)).

PPD/CCI

At Day 1 and Day 42 visits, patients will bring in and hand over their itch diaries to the study staff.

9.12 Transient Elastography (TE) or FibroScan®

Transient elastography (TE) e.g. FibroScan® will be conducted at the screening visit for subjects

PPD/CCI
If result shows a value ≥ 14.4 kPa, the subject won't be enrolled in the study.

9.13 Adverse Events

9.13.1 Definitions

Adverse Event

An adverse event (AE) is any untoward medical occurrence in a patient or clinical investigation subject administered a pharmaceutical product and which does not necessarily have to have a causal relationship with this treatment. An AE can therefore be any unfavorable and unintended sign or symptom, including clinically significant laboratory values and test results, concomitant illness, accident, or worsening of an existing medical condition.

The following should not be recorded as an AE if noted at screening:

- A pre-planned procedure for an illness included in the patient's medical history, unless the condition for which the procedure was planned has worsened since baseline. Please observe that complications to pre-planned procedures should be recorded as AEs.
- A pre-existing condition found as a result of screening procedures.

Any worsening in severity or frequency of a baseline concomitant illness or any new illness diagnosed in the trial period must be regarded as an AE.

Serious Adverse Event

A serious adverse event (SAE) is any adverse event that, at any dose:

- Results in death
- Is life-threatening. Life-threatening refers to an event in which the patient is at risk of death at the time of the event. It does not include an event that, had it occurred in a more severe form, might have caused death.
- Requires inpatient hospitalization or prolongation of existing hospitalization – Inpatient hospitalization includes an overnight admission.
- Results in persistent or significant disability/incapacity. Disability is defined as a substantial disruption of a person's ability to conduct normal life functions.
- Results in the birth of a child with a congenital anomaly/birth defect.
- Important medical events that may not result in death, be life threatening, or require hospitalization may be considered an SAE (when based upon appropriate medical judgment). These events may jeopardize the patient and may require medical or surgical intervention to prevent one of the outcomes listed above.

Adverse Reaction

An adverse reaction (AR) is any untoward and unintended response to a test drug that has been considered to have a causal relationship with the treatment.

Suspected Unexpected Serious Adverse Reaction

A suspected unexpected serious adverse reaction (SUSAR) is an adverse reaction that is serious and where the nature or severity of which is not consistent with information in the current Investigator's Brochure.

Abnormal Laboratory Value as an AE

An abnormal clinical laboratory value (i.e. any clinical laboratory abnormality or change that suggests a disease and/or organ toxicity and is of a severity that requires active management [i.e. change of test drug dose, discontinuation of test drug, medical treatment, more frequent follow-up or diagnostic investigation]), will be regarded as an AE. If clinical sequelae have been associated with a laboratory abnormality the diagnosis or medical condition should be reported (e.g. renal failure, hematuria) to replace the laboratory abnormality (e.g. elevated creatinine, urine RBC increased).

